3. STUDY SUMMARY

Title:	Automated Ultrasound Flow Monitoring for Maturation of Peripheral Arteriovenous Fistulae
Protocol Number:	2019-1
Design:	
This is a prospective, single arm, non-randomized, multi-center observational study to demonstrate the performance of the EchoMark and EchoSure devices in patients undergoing peripheral arteriovenous fistula creation for hemodialysis access.
 
Stage 1: EchoMark implantation at the time of fistula creation with scheduled follow up for EchoSure imaging of the fistula maturation process. This stage will produce EchoSure criteria for early prediction of maturation failure.
 
Stage 2: EchoMark implantation and imaging with EchoSure to prove the robustness of the fistula maturation failure criteria established in stage 1 and measure the effect on ultimate fistula maturation rates.

Study Duration:	
Projected enrollment of first patient: May 2020
 
Projected exit of final patient: December 2021

Primary Objective:	
Stage 1: The primary objective of the study is to collect data to verify the technology's performance in monitoring fistula maturation and understand the natural history of AV fistula flow physiology.
 
Stage 2: The primary objective of the study is to assess the ability of the EchoMark and EchoSure system to reduce the rate of failed fistula maturation.

Patient Population:	Patients undergoing upper extremity autologous arteriovenous fistula creation.
Sample Size:	
Stage 1: Up to sixty (60) patients will be enrolled.
 
Stage 2: Up to sixty (60) patients will be enrolled.

Number of Sites:	To be determined
Treatments:	
Stage 1: EchoMark soft tissue marking devices will be placed and monitored using the EchoSure system for 24 weeks or confirmed fistula maturation/failure has been declared by the attending vascular surgeon, whichever comes first.
 
Stage 1: EchoMark soft tissue marking devices will be placed and monitored using the EchoSure system for up to 52 weeks. Upon the decision by the attending surgeon that the fistula failure is confirmed or that monitoring is no longer clinically necessary patients will exit the study

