5. STUDY OBJECTIVES

Purpose

Stage 1: The primary objective of Stage 1 of the study is to collect data to verify the technology's performance in fistula monitoring. In Stage 1, EchoMark is implanted and monitoring is completed post-operatively. EchoSure data is then captured in an effort to establish normal ranges of the relevant variables in the context of appropriately maturing fistulae and their physiology, which is currently unknown.

Stage 2: The purpose of Stage 2 of the study is to evaluate the performance of the EchoMark and EchoSure (both FDA approved devices) as an ultrasound-based method of monitoring maturation of fistulae. The implant and ultrasound will be used as per IFU. The primary purpose of the study is to collect data on patient outcomes and assess whether or not the information generated from use of

EchoMark and EchoSure can decrease the fistula maturation failure rate and improve the patency of fistulas after up to a year.

Performance Goals

Stage 1:

Primary Performance Endpoint:

- Data collection to verify accuracy
- Data collection to understand the natural history of flow physiology in AV fistulas and classify fistulas that will fail

Primary Safety Endpoint:

- Procedure freedom from Serious Adverse Events (SAEs) during the EchoMark implantation procedure and subsequent post-operative period

Stage 2:

Primary Performance Endpoint:

- Failed fistula maturation rate

Secondary Performance Endpoints:

- Cumulative fistula patency at the end of 1 year
- Volumetric flow data
- Vessel caliber
- Total cost of episode of care

Primary Safety Endpoint:

- Procedure freedom from Serious Adverse Events (SAEs) during the EchoMark implantation procedure and subsequent post-operative care.

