7. STUDY POPULATION

Number of Patients

Stage 1: Up to sixty (60) patients will be enrolled and both men and women will

be eligible for inclusion. The estimated enrollment period is six months and patients will be followed until the fistula matures and is suitable for use in dialysis or it is ultimately considered non-salvageable by the vascular surgeon.

Stage 2: Up to sixty (60) patients will be enrolled and both men and women will be eligible for inclusion. The estimated enrollment period is twelve months and patients will be followed until then or the decision by the attending surgeon that the fistula failure is confirmed, or that monitoring is no longer clinically necessary patients will exit the study.

Intended Use

The EchoMark and EchoSure devices are intended to be used by a trained medical professional. The EchoMark device is intended to be a Single Use Device, used in a surgical operating suite or equivalent setting. The EchoSure ultrasound devices are reusable and may be used in the operating suite, a post-operative unit such as the ICU or patient floor, or a typical outpatient clinic. When used intraoperatively or in the presence of breached skin, the ultrasound transducer should be used with a sterile probe cover.

Inclusion Criteria

- Age > 18 years
- Patients presenting for upper extremity arteriovenous fistula construction with autologous tissue for the purpose of eventual hemodialysis access where the surgeon has selected EchoMark and EchoSure as the optimal method of vascular monitoring based on clinical assessment and plan
- Patient is able to sign informed consent and able to participate in all testing associated with this clinical investigation
- Women of childbearing potential have a negative pregnancy test

Exclusion Criteria

- Age <18 years old
- Patient unable to sign informed consent
- Patient participating in another investigational device or pharmacological study
- Prisoner or patient from vulnerable populations as defined in 45 CFR 46.

This study will not target the recruitment of any potentially vulnerable subjects. If vulnerable subjects who are educationally or economically impaired present for fistula creation, they will not be given the opportunity to participate in the study.

PATIENT WITHDRAWAL FROM THE STUDY

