Patients are free to withdraw consent at any time. Patients who wish to terminate their participation in the research will no longer receive EchoSure ultrasound examinations of their fistula and their data will be removed from the study.

8: STATISTICAL ANALYSIS

Stage 1:

We will recruit 60 patients for participation in this study who are planning to undergo elective construction of upper extremity autogenous hemodialysis access. The minimum sample size of 45 was determined assuming a 50% successful fistula maturation rate (based on past studies) to yield sufficient power to detect a difference in maturation between this cohort and the intervention cohort in the next aim. It also accounts for the quantity of patient volumes needed to develop a [REDACTED] based on our experience with EchoSure. Lastly, this provides sufficient power to detect a difference in fistula maturation success based on the flow rate (logistic regression power estimation; $\alpha = 0.05$, $\beta = 0.8$, OR 2.5 [from $\text{Pr}(H_0) 0.45$ and $\text{Pr}(H_1) = 0.65$]. As a buffer, based on institutional experience with clinical research and subject attrition a drop-out rate of 25% has been added to yield a total of 60 patients.

Using the EchoSure-derived conduit diameter and volumetric flow as observed values and Duplex-derived conduit diameter and volumetric flow as accepted values, the accuracy of EchoSure will be calculated. Logistic regression will be used to assess the correlation between successful maturation and EchoSure-derived values for flow and conduit diameter at two weeks. Cut points will be evaluated to establish EchoSure criteria for [REDACTED] [REDACTED]. Pearson's correlation will be performed on both EchoSure-derived and Duplex-derived values of volumetric flow and conduit diameter to determine correlation between EchoSure findings at two weeks and both EchoSure and Duplex findings at six weeks.

Stage 2:

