For this portion of the study, we will recruit an additional 60 patients planning to undergo elective construction of upper extremity autogenous hemodialysis access. Again, the EchoMark fiducial marker will be inset at the time of fistula creation. The minimum sample size of 45 (60 prior to 25% dropout factor) is powered to detect an approximate 25% reduction in all-cause fistula failure in the early postoperative period. A χ^2 power analysis was performed with $\alpha = 0.05$, $\beta = 0.8$ and standard-of-care fistula maturation success at 50% based on institutional experience and prior literature which ranges from 30-70% and EchoSure early intervention success based on the Muray-Cases results which showed a 78% success rate achieved by a novel program of pre-maturation ultrasonography and early intervention.

The nominal-by-interval association coefficient, Eta, will be calculated to determine the correlation between successful, unassisted maturation and EchoSure-derived values for flow and conduit diameter at two weeks. This will be compared to the similar findings of stage 1 using Student's t-testing and will validate the early maturation criteria derived from there. The association coefficient will be calculated to determine the correlation between successful, assisted maturation and EchoSure-derived values for flow and conduit diameter immediately following intervention. Pearson's correlation will be performed on both EchoSure-derived and Duplex-derived values of volumetric flow and conduit diameter to determine correlation between findings immediately following intervention and those at six weeks. [REDACTED]

Using χ^2 testing between the stage 1 and 2 cohorts, the benefit to maturation success of intervention based on early postoperative EchoSure examination will be determined.

9: PATIENT ENROLLMENT AND CONSENT

Method of Subject Identification and Recruitment

Patients will be identified and recruited by the surgeons participating in the study. Patients who have been scheduled for a fistula creation surgery will be identified as appropriate for study recruitment. The study details will be explained to identified patients and the consent process will begin for willing patients.

Informed Consent

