10. STUDY PROCEDURES AND METHODS

Patients undergoing fistula creation procedures will be identified. The study will be explained to these patients and informed consent for participation in the study will be obtained from willing patients. A small, FDA-approved tissue marker will be implanted prior to closure of wounds following the Instructions for Use on the FDA-approved labelling.

Stage 1: The fistula will be assessed with intermittent EchoSure examinations, sometimes during routine dialysis visits (maximum 3x/week) to minimize travel. This will conclude when the fistula has entirely matured and the patient begins hemodialysis via the fistula or when the vascular surgeon declares that the fistula has failed despite any and all salvage attempts.

Stage 2: Similar to stage 1 but with implementation of the normative values for relevant variables that resulted from the data collected in stage 1, with subsequent use of the EchoSure flow information in the vascular surgeon's decision making. This stage will also conclude when a year has passed and the fistula is functioning or when the vascular surgeon declares that the fistula has failed despite any and all salvage attempts or that monitoring is no longer clinically necessary.

Actions to Be Taken by Site Staff	Screening and pre-operative evaluation	Clinic Visits	Initiation of dialysis or fistula failure
Consenting	X		
Initial Enrollment Form		X	
Nurse Scan Form		X	
EchoSure Scan		X	
Standard Clinical Exam		X	
End of Trial Period Form			X

11: DATA COLLECTION, ANALYSIS, AND MONITORING

Adverse events are not expected in this study. Unanticipated problems will be reported and discussed with the principal investigator and research coordinator. Patients will be regularly monitored for signs of infection, inflammation or device extrusion. Should the implantable device require removal, it will be removed, and patient will be monitored with conventional methods. The research team will periodically review its protocols to ensure maximal patient safety and data validity.

Source Documentation

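### Stage 1 models maturation without setting rescued fistulas apart, while Stage 2 validates the resulting criteria on unassisted maturation

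*Combined protocol and SAP*

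**What the plan says.** The Study Summary (Section 3) gives the purpose of Stage 1: "This stage will produce EchoSure criteria for early prediction of maturation failure". Section 5 lists as an endpoint: "Data collection to understand the natural history of flow physiology in AV fistulas and classify fistulas that will fail".

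The Stage 1 analysis in Section 8 reads: "Logistic regression will be used to assess the correlation between successful maturation and EchoSure-derived values for flow and conduit diameter at two weeks". Cut points follow, but the words naming their target are blacked out.

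Three places say how Stage 1 ends for a patient:

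- Section 7 follows patients "until the fistula matures and is suitable for use in dialysis or it is ultimately considered non-salvageable by the vascular surgeon".
- Section 10 ends follow-up at dialysis through the mature fistula, or "when the vascular surgeon declares that the fistula has failed despite any and all salvage attempts".
- Section 3 monitors "for 24 weeks or confirmed fistula maturation/failure has been declared by the attending vascular surgeon, whichever comes first".

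In the Stage 2 part of Section 8, an Eta coefficient is calculated "to determine the correlation between successful, unassisted maturation and EchoSure-derived values for flow and conduit diameter at two weeks". It is compared with the corresponding Stage 1 results by a t-test, and this comparison is what validates the Stage 1 criteria. Assisted maturation has its own, separate analysis in Stage 2.

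**The concern.** Criteria meant to warn of failure early should be fitted to what happens to a fistula if nobody intervenes. Section 4 says that two weeks after surgery is the accepted time from which revision can be done, and the predictor scan is also at two weeks. Salvage can therefore fall between predictor and outcome. Stage 1 permits salvage, and nothing in its analysis text sets assisted maturation apart. A poorly flowing fistula that is revised and then matures enters the model as low flow with success.

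Two things are at stake. The flow association that Stage 1 is meant to detect may be diluted. And Stage 2 tests the criteria on a different outcome from the one they were built on, so neither agreement nor disagreement between the stages can be read cleanly. Section 10 carries the Stage 1 values into surgeons' decisions in Stage 2.

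**Working it through.** **The plan's own figure.** Inputs from Section 8: 50% against 78% maturation, alpha 0.05, power 0.80 (written there as beta). I take the test as two-sided without continuity correction.

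n = [1.960 × √(2 × 0.64 × 0.36) + 0.842 × √(0.50 × 0.50 + 0.78 × 0.22)]² / 0.28² = 44.9, so 45 per cohort. Then 45 / (1 − 0.25) = 60. The stated sizes reproduce, and this point does not affect them.

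**The logistic statement.** The plan gives OR 2.5 but no unit; I assume per SD of flow. The Hsieh approximation is n = (z_α + z_β)² / [P(1 − P)(ln OR)²].

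- With P = 0.50: 7.849 / (0.25 × 0.840) = 37.4, so 38 patients.
- Power at 45 = Φ(√(45 × 0.25) × 0.916 − 1.960) = Φ(1.11) = 87%.
- The probabilities quoted beside the OR, 0.45 and 0.65, imply (0.65/0.35) / (0.45/0.55) = 2.27, with about 78% power at 45.

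**Effect of counting rescued fistulas as successes.** Assumptions: standard-normal flow, 50% unassisted maturation, unassisted OR 2.5 per SD. If p is the unassisted probability at a given flow and s the share of would-be failures rescued there, the analysed probability is p + (1 − p)s. The logistic model is refitted to that outcome and power taken from the formula above.

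| Rescue (assumed) | Overall maturation | OR per SD | AUC | Power at 45 |
|---|---|---|---|---|
| none | 50% | 2.5 | 0.72 | 87% |
| 10%, at every flow | 55% | 2.2 | 0.70 | 77% |
| 10%, below-median flow only | 53% | 2.1 | 0.69 | 70% |
| 30%, at every flow | 65% | 1.9 | 0.67 | 55% |
| 30%, below-median flow only | 60% | 1.6 | 0.62 | 33% |

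Check of the fourth row: overall maturation is 0.50 + 0.50 × 0.30 = 0.65, and power is Φ(√(45 × 0.65 × 0.35) × ln 1.92 − 1.960) = Φ(0.12) = 55%.

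If the plan's 50% is instead maturation after salvage, the loss is larger. With rescue at below-median flow only, OR is 2.1 and power 69% at 10% rescue, and OR 1.4 and power 22% at 30%.

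**Cut points.** The direction of any shift depends on the rule.

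- *Fixed predicted risk.* With 30% rescued at every flow, observed failure risk is 0.7(1 − p). It reaches 50% where 1 − p = 0.714, that is logit p = −0.916 = −ln 2.5, or 1 SD below the mean. About 16% of fistulas are flagged instead of 50%.
- *Youden index.* Rescue at every flow leaves the cut where it was. Rescue at below-median flow only moves it to higher flow: +0.14 SD at 10% rescue and +0.44 SD at 30%.

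**The two outcomes side by side.** Stage 1 regression: maturation, unqualified. Stage 2 validation: maturation without assistance. No Stage 1 analysis of unassisted maturation is specified for the t-test to use.

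**The case against.** The salvage wording in Sections 7 and 10 governs when follow-up ends; it does not define the regression outcome, which Section 8 leaves undefined. The Stage 2 comparison with Stage 1 makes sense only if Stage 1 also uses unassisted maturation, so that may be what was meant. The blacked-out cut-point target could contain the qualifier. All of this is fair. But the regression sentence is intact and carries no qualifier, and an analyst following the text would count a rescued fistula as matured. If unassisted maturation was intended, the fix only states the intention.

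The dilution may also be modest. Section 4 says early ultrasound surveillance is not typical and that reimbursed Duplex comes at six weeks if maturation is absent, so heavy early rescue is not the documents' picture. At 10% rescue, power is still 70% to 77%. Heavy rescue would also push Stage 1 maturation well above the 50% the plan assumes. This stands, and it is why the size is given as a range.

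Two stronger readings are tempting. A reader might infer that the cut points move to lower flow, so that salvageable fistulas are classed as normal. That holds for a fixed-risk rule, but not for a Youden cut, and the visible text names no rule. A reader might also infer that scans after a revision enter the normal ranges. Section 5 ties those ranges to fistulas that are maturing appropriately and does not say that revised ones qualify.

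**Conclusion.** The concern holds in a limited form. As written, Stage 1 counts a revised fistula that matures as a success, and the Stage 2 validation then uses a different outcome. The mismatch needs no assumption about salvage rates; it follows from the text of Section 8.

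The dilution is firm in direction when salvage is equally or more likely at low flow. It could reverse if salvage went mainly to high-flow fistulas. Its size rests on an assumed 10% to 30% rescue and an assumed unit for the odds ratio: about 2.2 to 1.6 instead of 2.5, and power at 45 of 77% to 33% instead of about 87%. The documents do not give the Stage 1 salvage rate. Nothing can be concluded about which way the cut points would move.

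**What to change.** In the Stage 1 part of Section 8:

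- Make unassisted maturation the outcome for the logistic model and the cut points, matching Stage 2. Define it as reaching maturity with no earlier intervention to promote maturation.
- Report maturation after any salvage as a sensitivity analysis.
- Keep overall maturation for the chi-square test between the stages, where it is a reasonable outcome.
- Record the date and type of every intervention prospectively; otherwise the split depends on later chart review.

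The cost is analysis-plan wording and data-collection fields, with no extra scans or patients. The content of the forms is not shown, so some of this may already be collected.

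There is a statistical downside. The outcome then partly reflects surgeons' decisions to intervene. Some of those fistulas would have matured anyway, and if low flow prompts intervention the association is inflated. The plan's own Stage 2 outcome already has this weakness, since EchoSure data inform decisions there. Showing both outcomes brackets the effect: one may overstate the association, and the other is diluted by rescue.

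### No internal validation of the Stage 1 cut points is visible before they inform Stage 2 decisions, and the planned Stage 2 check does not test the cut points themselves

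*Combined protocol and SAP*

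**What the plan says.** Section 8, Stage 1 sets out two linked steps on the same cohort. First: "Logistic regression will be used to assess the correlation between successful maturation and EchoSure-derived values for flow and conduit diameter at two weeks". Then: "Cut points will be evaluated to establish EchoSure criteria for", where the text is blacked out. The minimum evaluable size is 45 at an assumed 50% maturation rate, and "a drop-out rate of 25% has been added to yield a total of 60 patients".

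The criteria are meant to be used. Section 10 describes Stage 2 as similar to Stage 1 but "with implementation of the normative values for relevant variables that resulted from the data collected in stage 1", with EchoSure flow feeding the surgeon's decisions. Section 6 says those decisions combine clinical data with EchoSure data.

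The plan also names a validation. Section 3 says Stage 2 is there "to prove the robustness of the fistula maturation failure criteria established in stage 1". Section 8, Stage 2 recruits a further 60 patients, calculates Eta between unassisted maturation and two-week flow and diameter, and compares it with the Stage 1 findings by Student's t-test as validation of the early criteria. Assisted maturation is analysed separately, against values taken just after intervention. One further sentence in that paragraph is blacked out.

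**The concern.** A cut point picked because it separates outcomes best in one small sample also fits that sample's noise. Sensitivity and specificity computed on the same patients are then biased upward. In the visible text nothing corrects for this between deriving the criteria and using them: no selection criterion, split sample, cross-validation, bootstrap or lock date. Stage 2 surgeons would therefore weigh EchoSure criteria whose reported accuracy may be overstated.

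A second cohort would normally settle the matter. Here two features stop it from doing so: the statistic chosen for the validation, and the fact that the Stage 2 outcome is influenced by the measurement being validated.

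**Working it through.** **Inputs from the documents (Section 8).** 45 evaluable patients per stage; 50% maturation, so 45 × 0.5 = 22.5, about 22 failures; two candidate predictors (flow and diameter at two weeks); odds ratio 2.5; alpha 0.05; β = 0.8, read as power 0.80; Stage 2 success 78%; dropout 25%.

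**The plan's own figure.** Two proportions, two-sided, pooled variance under the null, no continuity correction:

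n = [1.96 √(2 × 0.64 × 0.36) + 0.842 √(0.50 × 0.50 + 0.78 × 0.22)]² / 0.28² = (1.330 + 0.546)² / 0.0784 ≈ 44.9, so 45. Then 45 / 0.75 = 60.

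The stated 45 and 60 reproduce. For the logistic regression, with the odds ratio taken per SD, n = (1.96 + 0.842)² / [0.25 × (ln 2.5)²] ≈ 37.4, so 38, and 45 patients give about 87% power. The plan's two probabilities, 0.45 and 0.65, imply an odds ratio of (0.65/0.35)/(0.45/0.55) = 2.27, which needs 47. Neither calculation concerns the accuracy of a cut point. As a guide to precision, 16 of 22 failures detected has a 95% Wilson interval of 0.52 to 0.87.

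**Optimism of a searched cut point.** Assumptions not in the documents: one standard normal predictor, a logistic model with 50% maturation, the odds ratio per SD, and the cut point that maximises J = sensitivity + specificity − 1 over all observed values. There were 4,000 simulated samples; true J was read from 400,000 patients.

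| n | OR per SD | apparent J | true J | difference |
|---|---|---|---|---|
| 45 | 1.0 | 0.17 | 0.00 | 0.17 |
| 45 | 2.5 | 0.44 | 0.30 | 0.14 |
| 45 | 5.0 | 0.58 | 0.46 | 0.12 |
| 60 | 1.0 | 0.15 | 0.00 | 0.15 |
| 60 | 2.5 | 0.42 | 0.30 | 0.12 |
| 60 | 5.0 | 0.57 | 0.46 | 0.11 |

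At n = 45 and OR 2.5, sensitivity and specificity are each about 72% apparent and 65% true. Separate runs of this case put true J between 0.29 and 0.30. At OR 2.27 the result is 0.41 against 0.27. Taking the better of two independent null predictors raises apparent J at n = 45 from 0.17 to 0.23. With one null predictor, searching the central 80% of cut points gives a chi-square p below 0.05 in 39% of samples of 45, against a nominal 5%.

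**Effect of a bootstrap.** Repeating the search in each resample (100 resamples, 400 replicates, n = 45) lowers J from 0.44 to 0.34 at OR 2.5 (true 0.30), and from 0.17 to 0.07 with no association (true 0). A separate run gave about 0.33 at OR 2.5. Most of the optimism goes, but not all.

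**Does the Stage 2 validation test the cut points?**
- Eta relates maturation to flow or diameter as measured values. The cut point does not enter it, so agreement between stages says nothing about the sensitivity or specificity of the fixed criteria.
- Intervention changes the outcome. Illustration with assumed figures: take 100 fistulas, 50 of which would fail, and a cut point that is 66% sensitive and 66% specific. It flags 33 of the would-be failures and 17 of the others. If half of the 33 are rescued, observed sensitivity is 16.5/(16.5 + 17) = 49% and observed specificity is 33/(50 + 16.5) = 50%, with the cut point unchanged.
- Setting the 16.5 rescued fistulas aside restores specificity to 33/50 = 66% but leaves sensitivity at 49%. If instead every flagged fistula is intervened on and intervention counts as a failure, sensitivity becomes 50/(50 + 17) = 75% and specificity 33/33 = 100%. The answer depends on a handling rule that the visible text does not state.

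**The case against.** **The second cohort.** The criteria are not judged on Stage 1 patients alone. Stage 2 enrols new patients, is named as the validation, and separates assisted from unassisted maturation. This stands as a description of the plan. It does not close the gap, because no accuracy of the fixed cut points is reported and whether a fistula is assisted depends partly on the scan. The result would also arrive after the Stage 2 decisions have been made.

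**Redaction.** Text is blacked out right after the cut-point sentence and in the Stage 2 analysis. A reader might infer that the plan contains no optimism correction. The documents do not support that; they show only that none is visible.

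**The search rule is assumed.** Section 4 says ultrasound criteria for maturation failure already exist, and Sections 6 and 10 speak of normative ranges or values. Cut points fixed in advance would carry little or no optimism. This stands, and makes the magnitude conditional.

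**Stronger consequences.** A reader might expect the Stage 1 to Stage 2 comparison to show a fall due purely to optimism. The visible between-stage comparisons use Eta and maturation rates, neither of which is computed from the cut points, and any fall in accuracy would be mixed with the effect of intervention. A reader might also expect a bootstrap to reduce missed or falsely flagged fistulas. It corrects the reported accuracy and leaves the chosen cut point where it is. Section 6 also has surgeons weigh clinical data alongside the scan, so the criteria are not a stand-alone trigger.

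**Conclusion.** The point holds in conditional form. The visible plan derives cut points on about 45 patients and passes Stage 1 values to Stage 2 without internal validation, and the planned Stage 2 analysis does not measure how well the fixed cut points perform. If they are chosen by a best-Youden search, the Youden index would be overstated by about 0.11 to 0.17 over odds ratios of 1 to 5 per SD and 45 to 60 patients. At the plan's odds ratio of 2.5 and n = 45, that is about 0.44 apparent against 0.29 to 0.30 true. The size rests on the assumed search rule, the normal predictor and the per-SD reading of the odds ratio.

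The between-stage chi-square comparison of maturation rates remains analysable. What is affected is the reported accuracy of the criteria and the claim that Stage 2 validates them.

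**What to change.** In Section 8, Stage 1:
- State how the cut points are selected: candidate values, criterion, and how flow and diameter are combined.
- If the selection is data-driven, bootstrap the whole search over both predictors, for example with 1,000 resamples. Report optimism-corrected sensitivity and specificity with confidence intervals, and note that the correction removes most of the optimism, not all.
- Lock the cut points in a dated document before the first Stage 2 implant.

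In Section 8, Stage 2:
- Report sensitivity and specificity of the locked cut points, with intervals, alongside Eta.
- State in advance how fistulas that received an intervention are handled, and show the result under at least one alternative handling.

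The cost is some SAP text and a short program; no sample size changes. The downside is that reported Stage 1 accuracy becomes less favourable. If the blacked-out text already contains a selection rule or a validation step, the sponsor need only confirm it and add the Stage 2 items.
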